8.9.2. Work Productivity and Activity Impairment Questionnaire (WPAI)

WPAI will be assessed by the participant at study visits described in Table 1.

The WPAI questionnaire is an instrument to measure impairments in both paid work and unpaid work [Reilly, 2002]. It measures absenteeism, presenteeism as well as the impairments in unpaid activity because of health problem during the past seven days. It has been validated to quantify work impairments for numerous diseases such as asthma, psoriasis, irritable bowel syndrome, ankylosing spondylitis and Crohn's disease [Reilly, 2004; Reilly, 2010; Reilly, 2008]. In addition, the WPAI questionnaire has been used to compare work impairments between treatment groups in clinical studies and trials or between participants with different disease severity levels [Reilly, 2004; Reilly, 2010; Reilly, 2008; Revicki, 2007; Pearce, 2006; Chen, 2008].

The WPAI-GH consists of six questions: 1 = currently employed; 2 = hours missed due to health problems; 3 = hours missed other reasons; 4 = hours actually worked; 5 = degree health affected productivity while working (using a 0 to 10 VAS); 6 = degree health affected productivity in regular unpaid activities (VAS) [Reilly, 1993]. The recall period for the questions 2 to 6 is 7 days. Four main outcomes can be generated from the WPAI: 1) percent work time missed due to health for those who were currently employed; 2) percent impairment while working due to health for those who were currently employed and actually worked in the past seven days; 3) percent overall work impairment due to health for those who were currently employed; 4) percent activity impairment due to health for all respondents [Reilly, 2002]. For those who missed work and did not actually work in the past seven days, the percent overall work impairment due to health will be equal to the percent work time missed due to health.

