The overall visual analogue scale (VAS) symptoms score will be collected daily in the morning via the eDiary. Participants will be asked to rate their overall symptoms at their worst over the previous 24 hours. A scale from 0 (None) to 100 (As bad as you can imagine) will be used. The final VAS scores that are reported will be derived from the electronically captured score by dividing each score by 10 and will range between 0 and 10. This endpoint will be handled in the same way as the co-primary VRS endpoint, with daily data being collapsed into 4-week time periods as described in Section 6.3.4.2.

A nasal obstruction VAS score will also be collected daily in the morning via the eDiary at key time-periods during the study. The data from this endpoint will be collapsed into the expected time periods as described in Section 6.3.4.2.

The VRS composite scores will be derived for each day by taking the mean of the individual VRS scores for that day. All of the individual VRS scores contributing to a composite score must be non-missing in order to derive the mean.

All VRS endpoints will be handled in the same way as the co-primary VRS endpoint, with daily data being collapsed into 4-week time periods as described in Section 6.3.4.2.

The short-form-36 (SF-36) questionnaire consists of 36 self-administered questions that cover 8 health domains: physical functioning (PF), role physical (RP), bodily pain (BP), and general health (GH), vitality (VT), role emotional (RE), social functioning (SF), and mental health (MH) with a recall of 4 weeks. Certified scoring of the SF-36 survey will be performed using OPTUM TM software. The 8 domain scores are provided by the software. Scale scores range from 0 to 100 where higher scores indicate better quality of life.

The work productivity and activity impairment (WPAI) questionnaire is an instrument to measure impairment in paid and unpaid work and daily activities. Six questions will be collected at each visit including employment status, hours missed from work due to health problems and due to other reasons, hours actually worked, and how much health problems affected productivity and activity.

The following measures will be derived from the 6 WPAI-GH questions ranging from 0 (no impairment) to 100 (full impairment):

Derived Outcomes Derivation	Derived Outcomes Derivation
Work time missed due to health (%)	100 * Q2 / (Q2+Q4)
Impairment while working due to health (%)	10 * Q5

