Overall work impairment due to health (%)	100* Q2 / (Q2 + Q4) + [(1 - (Q2 / (Q2+Q4))) x
	(Q5 / 10)]
Activity impairment due to health (%)	10 * Q6

Note (each question with a recall of 7 days):

- Q1 = Currently Employed
- Q2 = Time (hours) missed from work due to health problems during the past seven days
- Q3 = Time (hours) missed from work due to other reasons during the past seven days
- Q4 = Time (hours) actually worked during the past seven days
- Q5 = Productivity affected by health problems while working during the past seven days
- Q6 = Ability to do regular daily activities affected by health problems during the past seven days

Participants not currently employed will only answer Q6. Participants who answer 0 to Q4 will not answer Q5.

If any of the responses used to derive a score are missing or if a participant is not currently employed then the relevant score (work time missed, impairment while working, overall work impairment) will be set to missing.

For those who missed work and did not actually work in the past seven days, the percent overall work impairment due to health will be equal to the percent work time missed due to health.

For SF-36 and WPAI-GH, the intercurrent event of surgery and initiation of a disease-modulating medication for CRSwNP will be handled under the composite strategy by assigning participants their worst observed score prior to the event. All other intercurrent events described under the primary estimand strategy in Section 1.1.2 will be handled using a treatment policy strategy.

For all responder endpoints, participants who undergo nasal surgery or initiate a disease-modulating medication for CRSwNP will be included in the analysis as non-responders for all time points following the event, whichever occurred first. For participants with missing baseline data, a responder status will not be derived. Participants with missing data at a particular post-baseline visit / timepoint will be treated as non-responders for that visit/ timepoint. All other intercurrent events described under the primary estimand strategy in Section 1.1.2 will be handled using a treatment policy strategy.

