# 4.4.2. Main analytical approach

Summary statistics by visit will be provided for the SF-36 and WPAI-GH endpoints.

Summary of responder status by visit will be provided for the 28-point SNOT-22 responder endpoint.

Summary statistics for change from baseline at the key time-periods when it was collected will be provided for overall VAS score.

The change from baseline endpoints related to VAS and VRS scores will be analyzed in the same way as the co-primary endpoints.

For the endpoint, achieving a meaningful decrease from baseline in their mean individual symptoms VRS and composite VRS from Week 49 through to Week 52 without first having nasal surgery (actual) or initiation of a disease-modulating medication for CRSwNP, the clinically meaningful VRS cut-points for mean individual symptoms VRS and composite VRS are as follows:

- Achieving a 1-point or greater decrease from baseline in nasal obstruction VRS total score at Week 52 without first having nasal surgery (actual) or disease-modulating medication for CRSwNP
- Achieving a 1-point or greater decrease from baseline in rhinorrhoea VRS total score at Week 52 without first having nasal surgery (actual) or disease-modulating medication for CRSwNP
- Achieving a 0.9-point or greater decrease from baseline in loss of smell VRS total score at Week 52 without first having nasal surgery (actual) or disease-modulating medication for CRSwNP
- Achieving a 0.8-point or greater decrease from baseline in facial pain VRS total score at Week 52 without first having nasal surgery (actual) or disease-modulating medication for CRSwNP

- Achieving a 1-point or greater decrease from baseline in mucous in throat VRS total score at Week 52 without first having nasal surgery (actual) or disease-modulating medication for CRSwNP
- Achieving a 0.8-point or greater decrease from baseline in composite nasal polyps symptoms VRS total score at Week 52 without first having nasal surgery (actual) or disease-modulating medication for CRSwNP
- Achieving a 0.8-point or greater decrease from baseline in composite CRS symptoms and facial pain VRS total score at Week 52 without first having nasal surgery (actual) or disease-modulating medication for CRSwNP

The remaining other endpoints will be analyzed as described below:

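### The SAP's formula for WPAI-GH overall work impairment multiplies only the absenteeism term by 100, so impairment while working adds at most 1 point instead of up to 100.

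*SAP*

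**What the plan says.** SAP section 4.4.1 derives four scores from the WPAI-GH questionnaire and states their common scale: "The following measures will be derived from the 6 WPAI-GH questions ranging from 0 (no impairment) to 100 (full impairment". In that table, work time missed is 100 × Q2/(Q2+Q4), impairment while working is 10 × Q5, and activity impairment is 10 × Q6. Here Q2 is hours missed because of health, Q4 is hours worked, and Q5 and Q6 are ratings.

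The fourth score, overall work impairment (%), is printed over two lines. The first reads "100* Q2 / (Q2 + Q4) + [(1 - (Q2 / (Q2+Q4))) x"; the second supplies the factor Q5/10 and closes the square bracket.

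Protocol section 8.9.2 gives the scale of Q5, "5 = degree health affected productivity while working (using a 0 to 10 VAS", and describes the outcome as "3) percent overall work impairment due to health for those who were currently employed". It states no formula of its own. For participants who missed work and worked no hours, the SAP sets a separate rule: "the percent overall work impairment due to health will be equal to the percent work time missed due to health".

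Change from baseline in WPAI-GH scores at Week 52 is listed among the 'other' endpoints. SAP section 4.4.2 plans a descriptive analysis only: "Summary statistics by visit will be provided for the SF-36 and WPAI-GH endpoints".

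**The concern.** The printed formula adds a percentage to a fraction. The first term runs from 0 to 100 and the second from 0 to 1. The score therefore cannot have the meaning the SAP gives it, because someone fully impaired at work who missed no hours is placed at the bottom of the scale.

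It also breaks a basic property of the measure. Overall impairment combines time lost with reduced output during the time worked, so it cannot be smaller than the impairment during the time worked. As printed, it often is.

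Two results are at stake. First, the reported overall score would be work time missed under another name, and a treatment effect on productivity at work would almost vanish from it. Second, for WPAI-GH the SAP assigns participants their worst observed earlier score after surgery or after starting disease-modulating medication. If the score is mis-scaled, the visit chosen as worst can be the wrong one.

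**Working it through.** **Inputs.** The printed formula, the scaling of the other WPAI-GH scores and the stated 0 to 100 range come from SAP section 4.4.1. The 0 to 10 scale of Q5 comes from protocol section 8.9.2. The 40-hour week (Q2 + Q4 = 40) is an illustrative assumption; the documents give no working hours.

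**Formulas.** Let a = Q2/(Q2+Q4) and p = Q5/10, both between 0 and 1.

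- As printed: 100a + (1 − a)p
- With 100 on the whole sum: 100[a + (1 − a)p]

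The at-work term is (1 − a)p in the first and 100(1 − a)p in the second. The ratio is exactly 100 whenever the participant worked and Q5 > 0, whatever the length of the week. The largest possible at-work contribution is 1 − a, at most 1 point, as printed. It should be 100(1 − a), which reaches 100 when no hours were missed.

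**Can the printed formula reproduce the stated range?** For full impairment at work with no absence (Q2 = 0, Q4 = 40, Q5 = 10), it gives 0 + 1 × 1 = 1, whereas the stated scale requires 100. The printed formula reaches 100 only through absence, when Q4 = 0.

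**Worked cases.**

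| Q2 | Q4 | Q5 | Work time missed (%) | Impairment while working (%) | Overall, as printed | Overall, 100 on whole sum |
|---|---|---|---|---|---|---|
| 0 | 40 | 5 | 0 | 50 | 0.5 | 50 |
| 0 | 40 | 10 | 0 | 100 | 1 | 100 |
| 4 | 36 | 3 | 10 | 30 | 10 + 0.9 × 0.3 = 10.27 | 10 + 27 = 37 |
| 8 | 32 | 4 | 20 | 40 | 20 + 0.8 × 0.4 = 20.32 | 20 + 32 = 52 |
| 20 | 20 | 5 | 50 | 50 | 50.25 | 75 |
| 20 | 20 | 0 | 50 | 0 | 50 | 50 |

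**Coherence.** A correctly scaled overall score is never below impairment while working, because a + (1 − a)p − p = a(1 − p) ≥ 0. Over a grid of Q2 = 0 to 40 and Q5 = 0 to 10 (41 × 11 = 451 combinations), the printed score falls below 10 × Q5 in 220. With 100 on the whole sum this happens in none. The 11 combinations with Q4 = 0 cannot arise as scored cases, since Q5 is then not asked. None of them is a violation, so the count among the rest is 220 of 440.

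**Effect on change from baseline.** A participant with no absence whose Q5 falls from 8 to 3 changes from 0.8 to 0.3 as printed, a change of −0.5. Correctly scaled, the change is 30 − 80 = −50.

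**Effect on the worst-observed rule.** Suppose two visits precede the intercurrent event.

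- Visit A (Q2 = 0, Q4 = 40, Q5 = 9): 0.9 as printed, 90 correctly scaled.
- Visit B (Q2 = 4, Q4 = 36, Q5 = 1): 10 + 0.9 × 0.1 = 10.09 as printed, 10 + 9 = 19 correctly scaled.

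The printed formula carries forward visit B; the correct one carries forward visit A.

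**The case against.** The strongest case on the other side concerns reach, not arithmetic. WPAI-GH is an 'other' endpoint outside the testing hierarchy of SAP section 2.1. It is summarised by visit, with no model, confidence interval or test planned. Three of the four WPAI-GH scores are scaled correctly, so an effect on productivity at work would still appear in the impairment-while-working score. Nothing changes when Q5 = 0, and participants who worked no hours are covered by the separate rule. All of this stands, and it caps the impact.

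It can also be said that the intended scale is obvious from the percent label, the stated range and the protocol's wording, so a programmer would probably use the right formula. That may be so, but the documents do not show what was programmed. The SAP names certified scoring software for SF-36 but none for WPAI-GH, so its table is the only specification given. A programmer who silently corrected it would depart from the SAP without a record.

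Finally, an outer pair of brackets could have been lost in typesetting, since the row wraps over two lines. This is unlikely: the printed brackets balance, so both an opening and a closing bracket would have had to go, and the neighbouring formulas are intact. A look at the typeset page would settle it.

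**Conclusion.** The concern holds. As written, the at-work part of overall work impairment is 100 times too small for every employed participant who worked and reported Q5 above 0. It contributes at most 1 point where up to 100 × Q4/(Q2+Q4) is due. The 100-fold factor and the 1-point ceiling follow from the formula and the 0 to 10 scale alone; only the worked examples and the grid count depend on the assumed 40-hour week.

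The harm arises only if the derivation is programmed literally. In that case one reported score is invalid and the worst-observed assignment for that score can be wrong. No co-primary, secondary, pooled or safety result is affected. It should be corrected because the rule as specified gives a wrong result, not because it threatens the trial's main conclusions.

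**What to change.** Replace the SAP entry for overall work impairment (%) with

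100 × { Q2/(Q2+Q4) + [1 − Q2/(Q2+Q4)] × Q5/10 }

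and leave the other three scores and the rule for participants with no hours worked as they are. Then check the programmed derivation against two or three hand-worked cases, for example Q2 = 0, Q4 = 40, Q5 = 10 giving 100, and Q2 = 8, Q4 = 32, Q5 = 4 giving 52. Confirm that the worst-observed assignment after surgery or disease-modulating medication uses the corrected score. The cost is one line in the SAP and one derivation in the analysis dataset; no new data are needed.

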# 4.4.2. Main analytical approach

Summary statistics by visit will be provided for the SF-36 and WPAI-GH endpoints.

Summary of responder status by visit will be provided for the 28-point SNOT-22 responder endpoint.

Summary statistics for change from baseline at the key time-periods when it was collected will be provided for overall VAS score.

The change from baseline endpoints related to VAS and VRS scores will be analyzed in the same way as the co-primary endpoints.

For the endpoint, achieving a meaningful decrease from baseline in their mean individual symptoms VRS and composite VRS from Week 49 through to Week 52 without first having nasal surgery (actual) or initiation of a disease-modulating medication for CRSwNP, the clinically meaningful VRS cut-points for mean individual symptoms VRS and composite VRS are as follows:

- Achieving a 1-point or greater decrease from baseline in nasal obstruction VRS total score at Week 52 without first having nasal surgery (actual) or disease-modulating medication for CRSwNP
- Achieving a 1-point or greater decrease from baseline in rhinorrhoea VRS total score at Week 52 without first having nasal surgery (actual) or disease-modulating medication for CRSwNP
- Achieving a 0.9-point or greater decrease from baseline in loss of smell VRS total score at Week 52 without first having nasal surgery (actual) or disease-modulating medication for CRSwNP
- Achieving a 0.8-point or greater decrease from baseline in facial pain VRS total score at Week 52 without first having nasal surgery (actual) or disease-modulating medication for CRSwNP

- Achieving a 1-point or greater decrease from baseline in mucous in throat VRS total score at Week 52 without first having nasal surgery (actual) or disease-modulating medication for CRSwNP
- Achieving a 0.8-point or greater decrease from baseline in composite nasal polyps symptoms VRS total score at Week 52 without first having nasal surgery (actual) or disease-modulating medication for CRSwNP
- Achieving a 0.8-point or greater decrease from baseline in composite CRS symptoms and facial pain VRS total score at Week 52 without first having nasal surgery (actual) or disease-modulating medication for CRSwNP

The remaining other endpoints will be analyzed as described below:

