Study 218079 Study 217095 Studies 217095 + 218079 Endpoints tested at α (0.05) Endpoints tested at α (0.05) Endpoints tested at $\alpha = \alpha^2 (0.0475)$ Nasal obstruction Total endoscopio Nasal obstruction Total endoscopio NP Score (Wk 52) VRS Score (Wks 49-52) NP Score (Wk 52) VRS Score (Wks 49- 52) Time to First Nasal Surgery Rhinorrhoea Rhinorrhoea VRS Score (Wks 49-52) VRS Score (Wks 49-52) (actual or entry on waiting list) Time to First Nasal Surgery (actual) Loss of smell VRS Score (Wks 49-52) VRS Score (Wks 49-52) Systemic Lund Mackay CT Lund Mackay CT Corticosteroid Use Score (Wk 52) Score (Wk 52) ACO-5 Score SNOT-22 Total (Wk 52) Score (Wk 52) Score (Wk 52) Nasal obstruction Nasal obstruction VRS Score (Wks 21-24) VRS Score (Wks 21-24)

Figure 4 Conceptualisation of Statistical Testing Strategy Across Studies 217095 and 218079

Note: Endpoint names in Figure 4 are abbreviated. Refer to Section 3 for full nomenclature of endpoints.

Total endoscopic

NP Score (Wk 26)

The treatment comparisons defined as part of the multiple testing strategy will be limited to the specified key comparisons shown in Figure 4. Other pairwise comparisons will be performed but will not form part of the multiple testing strategy. Analyses of other efficacy measures are nested under the secondary efficacy measures and no multiplicity adjustment is planned for these other efficacy endpoints.

If significance is achieved for both of the co-primary efficacy endpoints within this study, then the secondary endpoints within the study will be tested in a closed-testing manner using the pre-defined hierarchy. If significance is also achieved for each of the secondary efficacy endpoints within the study, then all other efficacy endpoints for the study will be tested without multiplicity adjustment.

If significance is achieved for both of the co-primary efficacy endpoints in both this study (217095) and study 218079, then the 4 secondary endpoints that are pre-specified to be a pooled analysis across both studies will be tested in a closed testing manner according to the pre-defined hierarchy. If significance is achieved at the α - α^2 (4.75%) level for all 4 of these endpoints, then all of the other efficacy endpoints that are pre-specified to be a pooled analysis across both studies will also be tested at the α - α^2 (4.75%) significance level without any multiplicity adjustment.

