To evaluate the efficacy of depemokimab 100 mg SC + SoC compared to placebo + SoC on composite symptom endpoints	
 
Change from baseline in the mean nasal polyps symptoms composite score (combining VRS scores for nasal obstruction, rhinorrhoea (runny nose), loss of smell, and mucus in throat) from Week 49 through to Week 52
 
Change from baseline in mean CRS symptoms and facial pain composite score (combining VRS scores for nasal obstruction, rhinorrhoea (runny nose), loss of smell, and facial pain) from Week 49 through to Week 52
 
Achieving a meaningful decrease from baseline in their mean individual symptoms VRS and composite VRS from Week 49 through to Week 52 without first having nasal surgery (actual) or disease-modulating medication for CRSwNP.
 

To evaluate the efficacy of depemokimab 100 mg SC + SoC compared to placebo + SoC on health-related quality of life	
 
Achieving an 8.9 point or greater decrease from baseline in SNOT-22 total score at Week 52 without first having nasal surgery (actual) or disease-modulating medication for CRSwNP
 
Achieving a 28 point or greater decrease from baseline in SNOT-22 total score at Week 52 without first having nasal surgery (actual) or disease-modulating medication for CRSwNP
 
Change from baseline in SF-36 Mental Component Summary (MCS) score, Physical Component Summary (PCS) score and eight domains at Week 52
 
Change from baseline in WPAI-GH scores at Week 52
 

Safety	
To evaluate the safety and tolerability of depemokimab 100 mg SC + SoC every 26 weeks, compared to placebo + SoC in patients with a diagnosis of CRSwNP	
 
Incidence of AEs/ Serious adverse events (SAEs)
 
Change from baseline in vital signs (heart rate, systolic and diastolic blood pressure, body temperature) at discrete timepoints during the 52-week period
 

Objectives	Endpoints
	
 
Change from baseline in ECG values at discrete timepoints during the 52-week period
 
Change from baseline in laboratory parameters (including haematological and clinical chemistry parameters) and hepatobiliary laboratory abnormalities at discrete timepoints during the 52-week period
 
Incidence of immunogenicity as measured by the presence of ADA and neutralising antibodies (NAb) to depemokimab
 

Pharmacokinetics and Pharmacodynan	nics

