# 2.1. Multiplicity Adjustment

The hypotheses to be tested are structured as shown in Figure 1. The co-primary endpoints will be tested first and if these comparisons are both significant at the 2-sided 5% level, testing will continue for the secondary endpoints within the study according to the testing procedure detailed in Figure 1. Testing of secondary endpoints will be carried out in a hierarchical manner, dependent on statistical significance having been achieved for the previous endpoint in the hierarchy. Other pairwise comparisons will be performed but are not part of the multiple testing strategy. Analyses of other efficacy measures are nested under the secondary efficacy measures and no multiplicity adjustment is planned for these other efficacy endpoints. The analyses for these other efficacy endpoints and some of the earlier time points for some of the co-primary and secondary endpoints are not adjusted for multiplicity and so nominal significance will be evaluated in a descriptive manner with these analyses using a 5% reference level.

A pre-specified pooled analysis of data from the ANCHOR-1 and ANCHOR-2 studies is planned for the secondary endpoints of time to first nasal surgery (actual or entry on waiting list) or disease-modulating medication for CRSwNP, time to first nasal surgery (actual) or disease-modulating medication for CRSwNP, proportion of participants requiring at least 1 course of systemic corticosteroids or disease-modulating medication for CRSwNP or nasal surgery (actual), and change from baseline in ACQ-5 score in participants with an ACQ score of >0.75 at baseline. This pooled analysis will be carried out after statistical significance is achieved for both co-primary endpoints within both studies. The closed-testing manner for the pre-specified pooled hierarchy is described further in the pooled SAP.

Figure 1 Conceptualization of Statistical Testing Strategy Across Studies ANCHOR-1 and ANCHOR-2

Note: Endpoint names in Figure 1 are abbreviated. Refer to Section 1.1 for full nomenclature of endpoints.

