## 4. STATISTICAL ANALYSES

#### 4.1. General Considerations

# 4.1.1. General Methodology

Unless otherwise stated, the Safety Analysis Set will be used for safety displays and the Full Analysis Set (FAS) will be used for all other displays. FAS-Modified and Safety-Modified analysis sets will be used for a selected number of displays as sensitivity analyses. FAS-China, FAS-Japan, Safety-China and Safety-Japan will be used for China and Japan specific outputs respectively. The Programming Specification document will provide more details.

Unless otherwise stated, all intercurrent events for primary, secondary, or other endpoints will be handled under the primary estimand strategy.

This SAP specifies the analytical approaches for the global submission requirements, unless otherwise specified. Further analytical considerations may be made for the regional displays (i.e. model convergence considerations) where appropriate.

The randomization is stratified based on occurrence of previous surgery for nasal polyps and unless otherwise stated, this variable will be included as a covariate in the statistical models. In the case of an incorrect stratification at the time of randomization, the actual stratum will be used rather than the randomized stratum.

Confidence intervals will use 95% confidence levels unless otherwise specified.

Unless otherwise specified, continuous data will be summarized using descriptive statistics: n, mean, standard deviation (std), median, minimum and maximum. Categorical data will be summarized as the number and percentage of participants in each category.

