## **Model Specification**

The conditional treatment effect for the responder analysis endpoints will be estimated using
a generalized linear mixed model with a logit link function and covariates of treatment group,
baseline score, log(e) baseline blood eosinophil count, region, previous surgery for nasal
polyps, visit and interaction terms for visit by baseline score and visit by treatment.

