## 4.12. Changes to Protocol Defined Analyses

There were no changes or deviations to the originally planned statistical analysis specified in the protocol.

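### SF-36 and WPAI-GH have a placebo-comparison objective, but the SAP plans only by-visit summaries and no pre-specified adjusted treatment difference or confidence interval

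*SAP*

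**What the plan says.** Both documents list change from baseline at Week 52 in SF-36 (MCS, PCS and eight domains) and in WPAI-GH as Other endpoints (protocol 3.1, SAP 1.1.1). The objective is comparative: "To evaluate the efficacy of depemokimab 100 mg SC + SoC compared to placebo + SoC on health-related quality of life".

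SAP 4.4.2 gives them one sentence: "Summary statistics by visit will be provided for the SF-36 and WPAI-GH endpoints". SAP 4.1.1 fixes what a summary contains: "continuous data will be summarized using descriptive statistics: n, mean, standard deviation (std), median, minimum and maximum".

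On testing, protocol 9.1.1 says that if each within-study secondary endpoint is significant, "then all other efficacy endpoints for the study will be tested without multiplicity adjustment". SAP 2.1 says of the other efficacy endpoints that "nominal significance will be evaluated in a descriptive manner with these analyses using a 5% reference level". SAP 4.12 states: "There were no changes or deviations to the originally planned statistical analysis specified in the protocol".

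SAP 4.4.1 does set an intercurrent-event rule for the two instruments. After nasal surgery or the start of a disease-modulating medication, a participant is assigned the worst score observed before the event.

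**The concern.** An objective framed as a comparison with placebo needs a between-group estimate. For these 14 scores the SAP names no effect measure, model or test. If the condition in protocol 9.1.1 is met, there is no defined test to carry out, and there is nothing to read against the 5% reference level in SAP 2.1.

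What is at stake is a pre-specified answer on generic quality of life and work or activity impairment. Without one, a reader must subtract unadjusted arm means, or a model must be chosen after the data are seen.

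**Working it through.** The plan states no figure on this point, so the check is mainly textual.

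**Step 1: is a contrast supplied anywhere else?** SAP 4.4.2 assigns models in two places.
- For continuous endpoints: "The change from baseline endpoints related to VAS and VRS scores will be analyzed in the same way as the co-primary endpoints". SF-36 and WPAI-GH are neither VAS nor VRS scores, so they fall outside this.
- For binary endpoints: "The conditional treatment effect for the responder analysis endpoints will be estimated using" a logit mixed model. The endpoints listed for it are the NP score responder, the VRS responders and the 8.9-point SNOT-22 responder. SF-36 and WPAI-GH have no responder definition.

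No other SAP section supplies an estimator for them.

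**Step 2: what does a summary contain?** SAP 4.1.1 lists n, mean, SD, median, minimum and maximum. It includes no difference, confidence interval or p-value.

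**Step 3: what surrounds the gap?**
- The intercurrent-event rule in SAP 4.4.1 settles scores after surgery or a disease-modulating medication, but no estimator follows from it.
- The same section treats a responder with a missing visit as a non-responder, and SAP 4.2.1 assumes missing at random for the co-primary endpoints. No rule for a missed visit is given for SF-36 or WPAI-GH beyond setting a score to missing.
- Where the SAP moved the 28-point SNOT-22 responder out of the model, its version history records the move. It records nothing similar for these two instruments.

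**Step 4: are the data there for a model?** The Schedule of Activities collects both instruments at Week 0 and at Weeks 8, 26, 40 and 52. One baseline and four post-baseline visits are enough for the repeated-measures model in SAP 4.2.2.

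**Step 5: how many scores?** SF-36: 2 + 8 = 10. WPAI-GH: 4. Total 14. Of the four WPAI-GH scores, three (work time missed, impairment while working, overall work impairment) are set to missing for anyone not employed. Only activity impairment applies to everyone.

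**Step 6: what precision would a contrast have?** The unadjusted 95% half-width in SD units is 1.96 × √(2/n), with n per arm.
- n = 118, the evaluable number in SAP 5, stated there for primary and secondary endpoints and borrowed here: 1.96 × √(2/118) = 0.255 SD.
- n = 125, all randomized: 1.96 × √(2/125) = 0.248 SD.
- n = 60, an assumption standing for an employed subset: 1.96 × √(2/60) = 0.358 SD.

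The SD here is that of the analysed change score. Neither document gives one, so the result is left in SD units. It describes the precision available and does not measure the omission itself.

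**The case against.** The best defence is that descriptive reporting is a deliberate choice for low-tier endpoints. These are Other endpoints outside the hierarchy. Protocol 8.9 also places both questionnaires under medical resource utilization and health economics. The SAP likewise only summarizes the 28-point SNOT-22 responder and four of the VRS responders. Disease-specific quality of life does get a full comparison: SNOT-22 total score is a secondary endpoint with an adjusted difference, CI and p-value. All of this stands, and it limits the weight of the point. It does not remove the mismatch with the objective or the absence of any statement that these endpoints are descriptive only.

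Four stronger readings are tempting, and the documents do not support them.
- **The protocol promises a test outright.** It does not. The sentence in 9.1.1 applies only if every within-study secondary endpoint is significant. SAP 2.1 carries no such condition, but it can be read as saying how to interpret whatever analyses are run.
- **SAP 4.12 is false.** That goes too far. Protocol 9.3 covers the most important endpoints and leaves detail to the SAP, so no specified model was dropped. What remains is a tension with one conditional sentence.
- **There will be no measure of uncertainty.** Means, SDs and n are reported, so a crude difference and interval can be worked out.
- **The summaries are raw completer data.** The composite rule in SAP 4.4.1 replaces scores after surgery or a disease-modulating medication.

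**Conclusion.** The point holds in a limited form. For 14 scores under a comparative objective, the plan provides no pre-specified, baseline-adjusted treatment difference, no confidence interval and no missing-visit handling to go with its intercurrent-event rule. The co-primary endpoints, the secondary hierarchy and the power are untouched.

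No reliable magnitude in points can be given. In SD units, an unadjusted interval would be about ±0.26 SD at 118 per arm, and wider for the work scores by an amount that depends on how many participants are employed. This assumes that the Programming Specifications, which are not part of the documents, do not define the contrast. Even if they did, the choice of estimator belongs in the SAP.

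The change is worth making because it is cheap and lets the trial answer its stated comparison.

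**What to change.** In SAP 4.4.2, analyse SF-36 MCS, PCS and the eight domains, and WPAI-GH activity impairment, with the SAP 4.2.2 MMRM using Weeks 8, 26, 40 and 52. Keep the intercurrent-event rule of SAP 4.4.1 and state the missing-at-random assumption for missed visits. Report the adjusted Week 52 difference with a 95% CI and a nominal p-value, labelled as outside the hierarchy.

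The three WPAI work scores need a separate decision. Employment is asked at each visit and can change after randomization, and a work score is undefined for someone not employed, so treating it as ordinary missing data would be wrong. Choose one of two options:
- report a contrast in participants employed both at baseline and at the visit, labelled as a subset analysis because membership depends on post-randomization status; or
- keep these scores descriptive and say so in SAP 4.12.

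If the sponsor prefers description for all 14 scores, the minimum is to state this in SAP 4.12 and to align the sentences in protocol 9.1.1 and SAP 2.1. That resolves the inconsistency but leaves the comparative objective without an estimate.

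The cost is a small amount of programming on an existing model and some additional nominal, unadjusted p-values. No new data are needed.
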